Quantitative data: We will use descriptive statistics (i.e., frequencies, means and standard deviation estimates) to describe the analytical sample. We will examine whether the implementation strategies (i.e., advisory board, use of REDCap handheld tablets, use of the PSC tool and an implementation coach) increases the number of children screened and referred to support services, compared to baseline. To do that, we will use methodology that accounts for repeated measures over time and that accounts for both within-person and across-person variation (i.e., Generalized linear mixed model (GLMM)) while controlling for clustering of patients within clinics and possible confounding by calendar time. *Our analysis will include sex as a biological variable, testing for a differential effect on outcomes by child sex.* We will report the magnitude of missing data and compare demographic and clinic characteristics and outcomes between observations with versus without missing data. In sensitivity analyses, we will perform multiple calculations (i.e., imputations) using fully conditional specification to obtain 10 complete datasets; summary estimates of intervention effects with 95% confidence limits over the 10 datasets will incorporate within- and between-dataset sampling variability.

Comparison of randomized intervention sites to non-randomized control sites

Due to the human and financial impact of COVID-19 epidemic, the randomized control periods had not implemented ACEs screening at the time of the pilot starting. We have identified two clinics that have implemented ACEs screening that are not part of the trial.

To obtain an additional non-randomized estimate of the intervention effect, we will compare:

- (1) the control periods in the randomized clinics to comparable time periods in the non-randomized clinics;
- (2) the intervention periods in the randomized clinics to comparable time periods in the non-randomized clinics.

We will use the same GLMM models as described above, with indicator variables for non-randomized vs randomized clinic, and randomized control vs intervention periods. Groups will be compared on ACEs screenings, and mental health referral rates.

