- a. Clinics using implementation strategies will have higher rates of mental health referrals compared to their referral rates before implementing the strategies.
- b. Clinics using implementation strategies will have higher rates of mental health referrals than clinics screening for ACEs and as part of the state funded CALQIC project, without the implementation strategies.
- c. Among children screened, ACEs screenings indicating medium and high risk will lead to mental health referrals at higher rates than screenings indicating low risk.
- d. Exploratory: Are there any differences between in the effect of the implementation strategies on referrals in different sub-groups (such as race, ethnicity, age and gender)?

[figure not shown]
3. Implementation outcomes

- a. Perceive feasibility, acceptability, and usefulness of the intervention will be sufficiently high (see Table 1).

Study design:

Changes to the original study design were needed to accommodate the negative impact that the COVID-19 pandemic had in the partner FQHC system. We conducted a stepped-wedge design (SWD) trial with three sites, with data collection divided into 7 10-week intervals. Study sites remained in the intervention phase for multiple intervals to allow additional data to be collected. In addition to the 3 study sites, 2 additional sites from the same health system served as comparison sites, implementing ACEs screenings without the support of the implementation strategies. See Figure 1 for the SWD schedule.

Figure 1. Stepped-wedge schedule for the ACEs pilot study.

Study sites and patient eligibility:

The study statistician originally selected five clinics from a pool of 16 clinics providing family medicine, pediatric, or primary care for children ages 0 to 5 years old and across five regions to maximize variation (e.g., clinic characteristics such as resources and size). Clinics were located in urban, suburban, rural, and frontier communities. The study PI and FQHC champions invited the identified clinics via email to an informational video session to introduce the study and provided study informational materials to the clinic manager.

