Reach	Measured as a proportion = number of eligible visits in a 10-week period divided by the number of PEARLS and clinical (BPSC/PPSC) screenings. Expect between 80%-92% of eligible children will be screened as threshold; based on pediatric screening studies in primary care. ^{7,8}	EMR system
Mental health referrals	Number of mental health referrals (behavioral analysis, behavioral health, care coordinator, care management, child development/development center or social work) divided by the total # of eligible children in a 10-week trial period. expect 11.4% increased referral rate based on a similar study ⁹ and using current referral rate of 3.8% to inform this threshold [per i2itracks report	EMR system
Changes in BPSC/PPSC	Mean score differences from eligible child visits in each 10-week period. Compare those means in pre vs post implementation periods. No threshold as we will test a two-tail hypothesis for this measure given mixed evidence on the impact of screening policies on access to care and clinical outcomes. ^{10,11} Even if a positive effect is not found, this information is still valuable for implementation and leadership.	EMR system

Measures		
Implementation leadership (ILS)¹²	12-item scale with four subscales measuring proactive leadership, knowledgeable leadership, supportive leadership, and perseverant leadership. Reliability for the total scale is strong ($\alpha=0.98$). An average score of 4+ used as threshold; 5-point Likert scale (not at all-very great extent). Subscale score is based on the mean score for the items; total score is the mean of the subscale scores ¹² ;	Staff provider
Implementation climate¹³	6-item scale measuring the strategic climate for the implementation of interventions. The average interrater agreement: $r^*wg (J) = 0.76$ for the group referenced scale. Items are rated on a 5-item Likert scale (completely disagree-completely agree). Average score of 4+ as threshold ¹³	Staff provider
Covariates		
Child characteristic	Variables include sex, self-identified race and ethnicity, age, language of preference for health care receipt, born in the USA. Note: EMR system does not report data on caregivers of child patients	EMR system

Statistical analysis:

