Descriptive statistics will be used to describe the sample of children and clinics. The sample will be described using counts and percentages, and treatment groups will be compared using chi-squared tests. We will calculate risk differences with confidence limits for each of our three groups of interest- the study clinics during the control period, study clinics during the intervention period, and the control clinics. For subgroup analyses exploring differences by child demographics, we will calculate risk differences within those subgroups (age, gender, race, and ethnicity).

The reach variable (proportions screened) will be analyzed using binary regression (a generalized linear model, specifying a binomially-distributed dependent variable and identity link function). Modified Poisson regression with robust variance estimation¹⁴ will be used to analyze mental health referrals to estimate adjusted risk differences. Both models will compare the intervention and control arms as the primary independent variable of interest. Possible covariates will include child's sex, age category (<18 months, 18-60 months), child's race (white, black, other/unknown), child's ethnicity (Latino, not Latino, unknown/not reported), language of preference, and study site; covariates will be included in their adjustment changes the intervention regression coefficient by more than 15%.

Models comparing the intervention and comparison clinics will be adjusted for the child's race and for the study site. Missingness in demographic data will be handled by including an 'unknown or not reported' category. Survey data will be analyzed using aggregated intra-class correlations (ICC) to assess within-group agreement, whether clinic care teams shared perceptions of readiness for change during the preparation phase, and implementation climate and leadership. ICC is the variance proportion attributed to care teams.¹⁵ Higher scores in these measures reflect higher organizational support for the translation of a new clinical practice into practice.¹⁶ An agreement of 0.70 or higher reflects an organizational measure.¹⁷

References

1. National Pediatric Practice Community. PEARLS FAQs. Accessed August 14, 2019. <https://nppcaces.org/faqs/>
2. Aware A. ACES Screening Clinical Workflows. Accessed June 15, 2020. <https://www.acesaware.org/wp-content/uploads/2019/12/ACE-Clinical-Workflows-Algorithms-and-ACE-Associated-Health-Conditions.pdf>

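### The SAP's within-clinic models have no calendar-time term and keep study site only under a 15% rule, unlike the protocol's model; this exposes the referral comparison (H2a) to secular trend

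*SAP*

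**What the plan says.** **Protocol.** Section V.c (Data Analysis, quantitative data) compares children screened and referred with baseline using a generalized linear mixed model, "while controlling for clustering of patients within clinics and possible confounding by calendar time".

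**SAP design.** Under Study design: "We conducted a stepped-wedge design (SWD) trial with three sites, with data collection divided into 7 10-week intervals". It adds: "Study sites remained in the intervention phase for multiple intervals to allow additional data to be collected". The crossover schedule is in Figure 1, which is not shown in the text available.

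**SAP hypotheses.** H2a reads: "Clinics using implementation strategies will have higher rates of mental health referrals compared to their referral rates before implementing the strategies". H1a makes the same before-and-after comparison for reach.

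**SAP models.** The Statistical analysis section uses a binomial model with identity link for reach and modified Poisson regression for referrals. It states: "Both models will compare the intervention and control arms as the primary independent variable of interest". The candidate covariates are sex, age category, race, ethnicity, language and study site. The selection rule is "language of preference, and study site; covariates will be included in their adjustment changes the intervention regression coefficient by more than 15" per cent. Neither calendar time nor the 10-week interval is a model term or a candidate. Site adjustment is unconditional only in the models against the comparison clinics (H1b and H2b).

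**Planning figures.** For referrals, Table 1 of the SAP says "expect 11.4% increased referral rate based on a similar study", "using current referral rate of 3.8% to inform this threshold".

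**The concern.** H1a and H2a set each clinic's later data against its own earlier data, so intervention status and calendar time are tied together by design. The protocol names this confounder and says it will be controlled. The SAP leaves it out, and because time is not on the candidate list, the 15% rule can never bring it in. Keeping site does not help, since the confounding lies within clinics.

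At stake is the meaning of a change in referrals, which the SAP lists among its primary outcomes. A sustained rise in referrals for any other reason would be credited to the strategies, and a sustained fall would hide a real effect. The documents describe an unsettled period (COVID-19, high staff turnover, a clinic closure), so drift is plausible, though nothing shows that it occurred.

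**Working it through.** The documents give no sample size, power or expected drift for H1a or H2a, so there is no planned figure to reproduce. The check asks how much of a common trend would appear as an intervention effect.

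**Inputs.** From the SAP: three clinics, seven intervals, referral baseline 3.8%, expected reach 80% to 92%. Assumed, because Figure 1 is not shown: distinct crossovers with intervention starting in intervals 2 to 6 (10 possible schedules), equal numbers per clinic-interval, and all seven intervals observed in each clinic.

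**Multiplier with site in the model.** Take a clinic with c control intervals and a linear drift of d points per interval.
- Mean interval number under intervention: (c + 1 + 7)/2 = (c + 8)/2.
- Mean interval number under control: (c + 1)/2.
- Difference: 7/2 = 3.5.

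The difference does not depend on c, so the false effect is 3.5 × d whatever the crossover times.

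**Other cases (least squares on the 21 clinic-intervals).**

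| Situation | False effect per unit of d |
|---|---|
| Site in model | 3.5 |
| No site | 2.6 to 3.3 |
| Site and interval indicators | 0 |
| Site in model, one or two clinics entering late | 2.4 to 3.5 |
| Site in model, cell sizes varying up to fivefold | about 2.9 to 4.1 |

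A trend that rises and falls back (0, 1, 2, 3, 2, 1, 0) largely cancels: −0.32 to +0.93 with site.

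**Referrals (H2a).** With an assumed d of 0.5 points:
- With site: 3.5 × 0.5 = 1.75 points.
- Without site: 2.6 × 0.5 = 1.3 to 3.3 × 0.5 = 1.65 points.

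The planned effect can be read three ways:
- A rise to 11.4% (11.4 − 3.8 = 7.6 points): 1.75/7.6 = 23%.
- A rise of 11.4 points: 1.75/11.4 = 15%.
- A relative rise of 11.4% (3.8 × 0.114 = 0.43 points): 1.75/0.43 = about 4 times the effect.

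**Reach (H1a).** If control reach was near zero, mimicking an 80-point gain would need 80/3.5 = 22.9 points of drift per interval. Over six steps that is 137 points, which is impossible for a proportion.

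**Price of time adjustment.** With site and interval indicators, the standard error is 1.6 to 2.2 times the site-only one for distinct starts (1.5 to 1.9 with a linear term). It can be larger if two clinics cross together: 2.3 to 2.8 for starts 2, 2, 3 or 3, 3, 4. If all three cross together, the intervention effect cannot be separated from the interval indicators.

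The adjusted model also assumes a constant effect. With no secular trend, and effects assumed by interval since crossover:

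| Effect in points | True average | Site only | Site and interval |
|---|---|---|---|
| 4, then 8 | 6.7 to 7.2 | 6.6 to 7.1 | 4.2 to 5.4 |
| 10, then 6 | 6.8 to 7.3 | 6.9 to 7.4 | 8.6 to 9.8 |
| 2, 4, 6, 8, 9, 10 | 4.2 to 5.9 | 4.1 to 5.6 | 0.5 to 1.3 |

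**The case against.** **No trend is shown.** A reader might infer that the H2a result is biased, or that a positive finding would be false. The documents do not support that: they give no secular trend in referrals, no sign and no size. The 0.5 points per interval is an assumption, and a transient rise and fall would leave little bias. This objection stands and limits the point to exposure.

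**Time adjustment may be the worse model.** A reader might infer that only the time-adjusted model should support a claim. That does not follow. Section II of the protocol (Activity 2) makes coaching weekly in the first 10-week period and less intense afterwards, so an effect that varies with time since crossover is a documented possibility. The adjusted model can then be badly wrong where the site-only model is nearly right. This stands and shapes the remedy.

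**A concurrent comparison exists.** H2b sets study clinics against two clinics in the same system, and section V.c of the protocol specifies comparable time periods. This is a useful partial check. It is not randomised, the SAP does not restate the period matching, and it does not repair H2a.

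**The departure may have a reason.** The SAP attributes design changes to COVID-19, and the protocol describes five clinics where the SAP has three. Both covers are dated July 20, 2024, but the protocol body has a version date of 05/10/2024 and may predate the SAP. A simpler model for three clinics is not arbitrary. Still, none of this explains the omission of calendar time.

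**Reach is hardly exposed.** A reader might extend the concern equally to H1a. Section V.c of the protocol says the control periods had not implemented screening when the pilot started, so a few points of drift are small against 80% to 92%. Reach is not wholly exempt, because step 4.8 of section V tells baseline clinics to follow the state screening requirements.

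**Conclusion.** The inconsistency is real and unexplained: the protocol controls for clinic clustering and calendar time, whereas the SAP has no time term for H1a and H2a and makes site optional. The consequence is an exposure to bias of unknown sign and size, chiefly in H2a. A sustained linear trend would pass into the estimate at 3.5 times its per-interval size with site in the model. That figure does not depend on the crossover times, but it does assume equal cells and all seven intervals in each clinic. The translation into referral points rests further on an assumed drift. The matter should be fixed. It does not show that the trial's referral result is wrong, and it carries little weight for reach if control-period reach was near zero.

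**What to change.** - Reconcile the SAP's Statistical analysis section with section V.c of the protocol, and give the reason for any departure that remains.
- Force study site into the H1a and H2a models and limit the 15% rule to child-level covariates.
- For H2a, specify and report a model with site and calendar time beside the site-only model. Use interval indicators, or a linear term if they do not fit. A linear term removes linear drift only; for the rise and fall above it leaves −1.1 to +2.2.
- Present any effect on referrals as exploratory: there are three clinics, two of which joined on capacity. If the two models disagree, call the question unresolved rather than evidence of no effect. State that the time-adjusted model assumes a constant effect, and do not make it the sole basis for a claim.
- Use H2b over comparable time periods as a further, non-randomised check on a shared trend.

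The cost is SAP wording and additional model runs on data already organised by 10-week interval. The time-adjusted estimate will have the wider interval set out above, may not be estimable with interval indicators if all clinics crossed together, and will lead to a more cautious conclusion.

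### In the within-clinic reach and referral models, covariates enter only through a 15% change-in-estimate rule, so the confounding that may stay in grows with the effect

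*SAP*

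**What the plan says.** The SAP, under Statistical analysis, models reach by binary regression "specifying a binomially-distributed dependent variable and identity link function", so the intervention coefficient is a risk difference. Modified Poisson regression "will be used to analyze mental health referrals to estimate adjusted risk differences"; the link is not stated.

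The candidate list begins "Possible covariates will include child's sex, age category (<18 months, 18-60 months), child's race (white, black, other/unknown" and goes on to ethnicity, language of preference and study site. The selection rule is "covariates will be included in their adjustment changes the intervention regression coefficient by more than 15" per cent (reading the second 'in' as 'if'). The SAP does not say whether the change is relative to the crude or the adjusted coefficient, or whether covariates are tested singly or jointly. It gives no absolute floor, no provision for a coefficient near zero, and no always-included set for the within-clinic models.

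One group of models is treated differently: "Models comparing the intervention and comparison clinics will be adjusted for the child's race and for the study site".

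The Protocol (V.c, Data Analysis) plans a mixed model that accounts for clustering within clinics and for confounding by calendar time. Calendar time is not on the SAP's candidate list.

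**The concern.** The rule uses the treatment estimate to decide how that estimate will be adjusted, and its threshold scales with the estimate. A given confounder is removed when the effect is small and kept when the effect is large, although the bias in percentage points is the same.

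This matters most for reach. The SAP's Table 1 says "Expect between 80%-92% of eligible children will be screened as threshold", while the Protocol says that "the randomized control periods had not implemented ACEs screening at the time of the pilot starting". The expected difference is therefore large, and so is the tolerance.

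Some confounding is plausible here. Control and intervention periods fall at different calendar times. The SAP (Study sites and patient eligibility) also reports that, of the three clinics that finished, one was randomly selected and two joined because they had capacity. At stake are the size of the adjusted risk differences and the honesty of their confidence limits.

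**Working it through.** The plan gives no figure to reproduce; the 15% is a decision rule. The checks below show what it lets through.

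**1. Tolerated shift = 0.15 × crude risk difference**

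Inputs: expected reach of 80%-92% (SAP Table 1) and a baseline referral rate from "using current referral rate of 3.8% to inform this threshold". Control-period reach is not stated, so 0% and 40% are assumptions. The expected referral increase of 11.4% can be read three ways.

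| Scenario | Risk difference (points) | Tolerated shift (points) |
|---|---|---|
| Reach 0% to 80% | 80 | 0.15 × 80 = 12.0 |
| Reach 0% to 92% | 92 | 0.15 × 92 = 13.8 |
| Reach 40% to 80% | 40 | 0.15 × 40 = 6.0 |
| Referral 3.8% to 11.4% | 7.6 | 0.15 × 7.6 = 1.14 |
| Referral 3.8% to 15.2% | 11.4 | 0.15 × 11.4 = 1.71 |
| Referral, 11.4% relative rise | 0.433 | 0.15 × 0.433 = 0.065 |

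If the change is measured against the adjusted coefficient, the three reach tolerances become 10.4, 12.0 and 5.2 points.

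For referrals the scale also matters. If the tested coefficient is a log risk ratio, then for 3.8% to 11.4% the ratio is 3 and the log is 1.099. A 15% drop gives exp(0.85 × 1.099) = 2.54, hence a risk difference of 3.8 × 1.54 = 5.87 points instead of 7.6. That is a 23% fall. For 3.8% to 15.2% the fall is 25%.

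**2. The same confounder at different effect sizes**

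Assumptions: baseline 5%, covariate prevalence 35% v 65%, covariate effect 25 points. The bias is 0.25 × 30 = 7.5 points.

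- True difference 60: crude 67.5, tolerance 0.15 × 67.5 = 10.1, so it normally stays out.
- True difference 10: crude 17.5, tolerance 2.6, so it enters.
- True difference 0: crude 7.5, tolerance 1.1, so it enters.

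In simulation (4,000 runs, linear risk-difference model) it entered in 7.5% of runs with 450 children and 0.7% with 1,500 when the true difference was 60. The remaining bias was 6.8 and 7.4 points. At 10 or 0 it entered in 100% of runs. The 450 is the Protocol's REDCap subset; 1,500 is an assumed larger EMR sample.

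**3. Interval coverage with a large effect**

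Assumptions: 300 per group, control rate 20%, true difference 50 points, covariate effect 15 points, robust standard errors.

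| Prevalence, control v intervention | Bias if omitted (points) | Tolerance (points) | 95% CI coverage under the rule |
|---|---|---|---|
| 30% v 70% | 0.15 × 40 = 6.0 | 0.15 × 56 = 8.4 | about 57% |
| 40% v 60% | 0.15 × 20 = 3.0 | 0.15 × 53 = 7.95 | about 85% |
| 45% v 55% | 0.15 × 10 = 1.5 | 0.15 × 51.5 = 7.7 | about 92% |

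With the covariate always included, coverage is about 95%. In the first row the rule admitted it in about 11% of runs and left a mean bias of about 5 points.

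**4. Near a null effect**

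With no true effect, a 3.8% baseline, 300 per group and five irrelevant covariates tested singly, at least one enters in about 33% of runs if prevalences are balanced at 50%, and about 70% if they are 45% v 55%. With balanced covariates, coverage was 95.1% under the rule and 94.7% with all five fixed, without bias.

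**5. Study site**

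In an illustration with three sites, assumed baselines of 30%, 20% and 10%, staggered crossover and a true difference of 40 points, the estimate was 47.7 without site and 40.0 with it. The 15% rule admitted site in 61% of runs.

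None of these simulations includes clustering within clinics.

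**The case against.** The strongest reply is that a closed candidate list with a numerical threshold is itself pre-specified, and that the damaging scenarios are assumed. The within-clinic contrast is between periods in the same clinics, so a 40-point shift in a child characteristic is extreme. At milder imbalance coverage is 85% or 92%. The SAP also already plans risk differences with confidence limits outside the regression models, so an unadjusted estimate is largely available. These points stand, and they limit the size of the concern. They do not justify a threshold that widens with the effect.

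A reader might infer several stronger things that the documents do not support:

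- **That the rule governs every adjustment.** The comparison-clinic models, which serve hypotheses 1b and 2b, have race and study site fixed.
- **That admitting irrelevant covariates near zero does serious harm.** It makes the model data-dependent, but the check found no bias or coverage loss with balanced covariates. The 70% entry rate requires the 45% v 55% imbalance.
- **That several small confounders would all be missed.** Take four confounders worth 1 point each on a true 8-point effect. The crude estimate is 12, and each single adjustment moves it by 1/12 = 8%, so none enters and the effect is overstated by half. Tested jointly, the shift is 4/12 = 33% and all enter. The SAP does not say which applies, so this shows ambiguity, not failure.
- **That a reach finding could reverse.** A true 50 points read as about 55 leaves the directional hypothesis 1a intact; its size and interval are affected.
- **That the within-clinic contrast has no randomisation at all.** The SAP describes how clinics were selected, and the Protocol still calls the study sites randomised. Neither account settles how crossover order was assigned.

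**Conclusion.** The concern holds for the within-clinic reach and referral models, and in part for the comparison-clinic models, where sex, age category, ethnicity and language are not in the fixed set. The rule tolerates a shift of 6 points in reach for an assumed 40% to 80% change, and 12.0 to 13.8 points from an assumed 0% to 80%-92%. The resulting loss of coverage runs from slight (about 92%) to severe (about 57%), depending on an imbalance that the documents do not report. For referrals the tolerance is 0.065 to 1.71 points, depending on how the 11.4% is read and provided the rule is applied on the risk-difference scale.

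Control-period reach, group sizes, covariate strengths and prevalences are assumptions. The tolerance arithmetic needs only the crude effect. This is a change that should be made, not a flaw that voids the analysis.

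**What to change.** Remove the 15% rule as the primary selection method. In the within-clinic reach and referral models, pre-specify and always include study site, sex, age category, race, ethnicity, language of preference and calendar period. In the comparison-clinic models, add the remaining child covariates and calendar period to the race and site terms already there. Print the unadjusted estimate beside each adjusted one. If a change-in-estimate rule is kept as a sensitivity analysis, state its scale, its denominator and whether covariates are tested jointly.

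Study site must not be lost in this edit. Deleting the rule and fixing only the five child covariates would close the one route by which site can now enter the within-clinic models, and the site illustration shows that this could worsen bias.

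The cost is mainly SAP wording. The child covariates come from the EMR, and missing demographics already have their own category. Three sites add two terms and seven 10-week intervals add up to six, so expect some loss of precision. The identity-link reach model may fail to converge, particularly if control-period reach is near zero, and the referral model may have few events per covariate. The SAP should therefore name a fallback, such as a linear risk-difference model with robust variance.

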ACCORDS

ADULT AND CHILD CENTER FOR OUTCOMES
RESEARCH AND DELIVERY SCIENCE

UNIVERSITY OF COLORADO
CHILDREN'S HOSPITAL COLORADO

Supporting the Implementation of a State Policy on Screening for Adverse Childhood
Experiences (ACEs) in Federally Qualified Health Centers (FQHC).

Statistical Analysis Plan

NCT: 04916587

Date: 7.20.2024

Statistical Analysis Plan

Title of Study: Supporting the Implementation of a State Policy on Screening for Adverse Childhood Experiences (ACEs) in Federally Qualified Health Centers (FQHC)

NIMH Study ID Number: R21MH123835

Clinical Trial Number: NCT04916587

Sponsor: Study funded by the National Institute of Mental Health.

Principal Investigator: [name] [name].

Summary and research objective(s):

Screenings for Adverse Childhood Experiences (ACEs) promote early identification of toxic stress and potential trauma, allowing for intervention and possible amelioration of detrimental effects of the ACEs. The state of California enacted a 2020 fee-for-service healthcare policy, ACEs Aware, reimbursing clinics for annual ACEs screenings during well-child visits, but did not provide guidance on screening implementation. This study aims to test the effectiveness and acceptability of a multifaceted implementation strategy for implementing ACEs screenings, in partnership with a Federally Qualified Health Center (FQHC) system in California that adopted the ACEs Aware policy in August of 2020.

The proposed strategy is comprised of personnel training (e.g., Trauma-informed care), integrated technology with a customized screening scoring and aligned service referral algorithm, team-based screening workflows, ongoing care team coaching, and peer support. Significant changes to the original study protocol were needed to accommodate the negative impact that the COVID-19 pandemic had in the partner FQHC system.

Hypotheses

1. ACEs screenings

- a. Clinics using implementation strategies will have higher rates of REACH of ACEs screenings compared to their screening rates before implementing the strategies.
- b. Clinics using implementation strategies will have higher rates of REACH of ACEs screenings than clinics screening for ACEs and as part of the state funded CALQIC project, without the implementation strategies.

- c. Exploratory: Are there any differences between in the effectiveness of the implementation strategies in different sub-groups (such as race, ethnicity, age and gender)?

2. Referrals to mental health services

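### Adjusting for study site makes the adjusted comparison of intervention and comparison clinics (hypotheses 1b and 2b) impossible to estimate

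*SAP*

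**What the plan says.** Hypotheses 1b and 2b in the SAP compare different clinics. For reach: "Clinics using implementation strategies will have higher rates of REACH of ACEs screenings than clinics screening for ACEs". For referrals: "Clinics using implementation strategies will have higher rates of mental health referrals than clinics screening for ACEs". The SAP's Study design section describes three stepped-wedge clinics followed over seven 10-week intervals, and adds that "2 additional sites from the same health system served as comparison sites, implementing ACEs screenings without the support of the implementation strategies".

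The Statistical analysis section specifies a binomial GLM with identity link for reach and a modified Poisson model with robust variance for referrals. It says "Both models will compare the intervention and control arms as the primary independent variable of interest". Study site appears in the list of possible covariates beside sex, age, race, ethnicity and language, subject to a 15% change-in-coefficient rule. A separate sentence then fixes the adjustment for the between-clinic models without that rule: "Models comparing the intervention and comparison clinics will be adjusted for the child's race and for the study site". No random effect is mentioned. The same section also plans unadjusted estimates: "We will calculate risk differences with confidence limits for each of our three groups of interest".

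Protocol section V.c gives a different model for this comparison: "We will use the same GLMM models as described above, with indicator variables for non-randomized vs randomized clinic, and randomized control vs intervention periods". The models it refers to are generalized linear mixed models "controlling for clustering of patients within clinics and possible confounding by calendar time".

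**The concern.** A covariate can be adjusted for only if both groups being compared occur within its levels, or if the model borrows information across levels. Here no clinic supplies data to both sides of 1b or 2b. With one fixed indicator per clinic, the group effect and the clinic effects cannot be separated, however many children are observed.

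Reach and referral rates are the SAP's primary outcomes, and 1b and 2b are not labelled exploratory, whereas 1c and 2d are. If software prints a site-adjusted figure anyway, that figure may depend on coding choices unrelated to the data. Alternatively, it may answer 1a or 2a while being reported under 1b or 2b.

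**Working it through.** The documents give no numerical result for this comparison, so there is nothing to reproduce. The check concerns whether the model can be estimated.

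**Inputs.** From the SAP: 3 study clinics, 2 comparison clinics, 7 intervals. Assumptions: Figure 1 is not shown, so each study clinic's first intervention interval was allowed to be any of 2 to 7, giving 6 × 6 × 6 = 216 schedules. Comparison clinics are taken as observed throughout.

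**Rule.** A contrast is estimable only if adding it as a row to the design matrix leaves the rank unchanged.

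**Why it fails.** Number the study clinics 1 to 3 and the comparison clinics 4 and 5. Then (comparison-clinic indicator) = (site 4 indicator) + (site 5 indicator). The dependency lies in the linear predictor, so the link function, robust variance and sample size do not affect it.

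**Rank results, identical in all 216 schedules:**

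| Model | Columns | Rank | Intervention minus comparison |
|---|---|---|---|
| Two groups + site | 1+1+4 = 6 | 5 | not estimable |
| Three groups + site | 1+2+4 = 7 | 6 | not estimable |
| Three groups + site + interval | 1+2+4+6 = 13 | 12 | not estimable |
| Three groups + interval, no site | 1+2+6 = 9 | 9 | estimable |

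In the three-group model with site, intervention minus control (1a and 2a) remains estimable. Adding race (3 levels, 2 more columns) was checked for crossovers at intervals 2, 3 and 4. With site the results were 7 of 8 (two groups) and 8 of 9 (three groups). Without site they were 4 of 4 and 5 of 5. Coding both comparison clinics as one site level also fails (two groups with race: 6 of 7).

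**Pooled-arm reading.** Suppose a single arm variable sets intervention periods against everything else, with site adjustment and no time terms. The model is full rank (6 of 6), but the comparison clinics never change arm, so they contribute nothing to the coefficient. Assume referrals rise from 3% to 11% in the study clinics:

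| Assumed comparison-clinic rate | Fitted coefficient | Difference that 2b asks about |
|---|---|---|
| 1% | 11 − 3 = 8 points | 11 − 1 = +10 points |
| 11% | 8 points | 11 − 11 = 0 points |
| 40% | 8 points | 11 − 40 = −29 points |

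**What software might print.** Assume reach of 85, 75 and 65% in the study clinics and 55 and 35% in the comparison clinics. The difference between the group means is 75 − 45 = 30 points. A routine that keeps every column of the deficient two-group model picks the solution with the smallest sum of squared coefficients.

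- With clinic 1 as reference, and b the group coefficient, the intercept is 0.85 − b and the two comparison-site coefficients are b − 0.30 and b − 0.50. Minimizing (0.85 − b)² + b² + (b − 0.30)² + (b − 0.50)² gives b = (0.85 + 0.30 + 0.50)/4 = 0.4125.
- Clinic 2 as reference: (0.75 + 0.20 + 0.40)/4 = 0.3375.
- Clinic 3: (0.65 + 0.10 + 0.30)/4 = 0.2625.
- Clinic 4: (0.30 + 0.20 + 0.10)/4 = 0.15.
- Clinic 5: (0.50 + 0.40 + 0.30)/4 = 0.30.

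An identity-link binomial fit (crossovers at intervals 2, 3 and 4; 100 visits per clinic-interval, assumed) returned these same five values. Fitted proportions were identical, and printed standard errors ran from 0.013 to 0.019. The last value equals the 30-point difference only by coincidence.

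**The case against.** The strongest reply concerns the premise. The SAP never says that site enters as fixed indicators, one per clinic. Its Study design section uses the term study sites for the three trial clinics, so the adjustment could mean a study-versus-comparison indicator alongside the arm variable. That matches the Protocol's coding and is estimable (rank 3 of 3, or 9 of 9 with intervals). This reading is possible but strained, because the same Statistical analysis section lists study site among ordinary child-level covariates. If it was intended, the SAP has to say so.

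A second reply is that the Protocol's mixed model makes the contrast estimable, and the two documents carry the same cover date. That is correct, but the SAP names different models and carries over neither the clinic clustering nor the calendar-time adjustment.

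Some limits on the illustrations do stand. The spread from 15 to 41 points comes from one kind of software behavior; other programs would drop a column or warn. The statement that the pooled coefficient is only the before/after change holds without interval terms. With them, comparison-clinic trends enter: in a check with assumed trends of 0, 1 and 2 points per interval, it was 8.0, 5.5 and 3.0 points. It still would not be the 2b difference.

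On importance, the Protocol presents this as an additional non-randomized estimate in a pilot, and an unadjusted between-group estimate survives. That limits the damage to the adjusted analysis, which is nonetheless the one the SAP prescribes.

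**Conclusion.** The concern holds, and the plan must be changed. With site as fixed indicators, which is the natural reading of the SAP's models, the adjusted contrast for 1b and 2b is not estimable under any of the 216 schedules. The pooled-arm version that can be fitted answers a different hypothesis. The rank result needs no assumption about event rates, visit numbers or crossover times, only that every clinic lies wholly on one side of the comparison. The illustrative percentages are assumptions and show consequences only. The conclusion does not extend to the unadjusted three-group risk differences, to 1a and 2a, or to a mixed model with clinic as a random effect.

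**What to change.** Remove study site as a fixed covariate from the 1b and 2b models; this alone restores estimability. In addition, to bring the SAP into line with Protocol section V.c:

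- Compare intervention intervals with the same calendar intervals in the comparison clinics, adjusting for interval and child covariates.
- Account for clinic either through clinic-level summaries or through the clinic clustering of the Protocol's mixed model. State which, and reconcile the two documents.
- A site-and-interval difference-in-differences for referrals may be added, but only if labelled as a change-over-time estimand and not as the test of 2b.

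The cost is SAP wording and two re-run models, with no new data. The drawback is precision. With 3 + 2 − 2 = 3 between-clinic degrees of freedom, the 95% critical value is 3.18 in place of 1.96, so limits will be wide. The comparison also remains non-randomized.
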